^a Childbearing potential to be defined as women who are not yet post-menopausal who are not consistently utilizing an acceptable form of contraception. Acceptable forms of contraception to include hormonal methods such as oral contraceptives, patches, injections, vaginal ring, or implants, hormonal or copper intrauterine device, or history of surgical sterilization including tubal ligation or hysterectomy.

screening assessments will have the chance to review any questions with the study staff, as well as a recap of the follow-up schedule, and they will then receive their randomization assignment.

Recruitment efforts will be made by working with Mayo Clinic's Research Recruitment Services to develop marketing materials including a recruitment flyer in both print and digital formats, a social media recruitment plan leveraging Mayo Clinic's enterprise social media accounts for recruitment and other potential tactics to be determined after recruitment begins, directed towards the goal of boosting minority inclusion to be at least representative of the local population. Data will be pulled during the time of IRB submission and included to establish general targets justifying Exclusion #35 to help reserve spots for enrollment that are in-line with a representative population if they are not met by a certain threshold. At the time of this writing, Rochester, MN has demonstrated approximately 10% minority population.

Randomization

Participants will be randomly assigned to treatment or control group with a 1:1 allocation per a computer-generated randomization using variable block randomization.

Participants will be blinded to the results of randomization. They will remain blinded until the end of the study, or if there is medical or surgical safety concern. If any SAEs occur, subjects may be unblinded as defined by the Clavien-Dindo Grade III or above. Unblinding of subjects will be reported to IRB per local site IRB guidelines, if not meeting the criteria above. Measures will be taken to minimize or avoid bias in the study using "masking/blinding procedures." Randomization assignment will be recorded in the EDC and subject tracking, but will not be recorded within the EMR to reduce clinical team exposure to their randomized status for follow-up care. Research teams will not be blinded to the randomization results. Subjects will be asked to confirm with their study team if they have become aware of the procedure.

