Weight, Height (Screening only), BMI, Waist and Hip Circumference Form	X		X		X	X	X	X	X	X	X	X	X
Vital Signs Form	X		X		X	X	X	X	X	X	X	X	X
Adverse Events Form			X	X	X	X	X	X	X	X	X	X	X
Medication Form	X		X	X	X	X	X	X	X	X	X	X	X
Randomization (ESG vs Hybrid ESG/APC) †		X											
EGD			X							X			
MRI	X										X		
Gastric emptying scintigraphy***	X										X		
Post-enrollment Nutrition/Exertion/Satiety counseling and assessment † †		X			X	X	X	X	X	X	X	X	
Subject Satisfaction Questionnaire													X
Inter-observation of EGD										X			

* Performed by Investigator or delegated medically qualified team member

** Females of childbearing potential only

***POC Urine Pregnancy Test required 48 hours prior to procedure (if not within window from blood test)

+ CBC, electrolytes, BUN, creatinine, HbA1c, fasting blood sugar, fasting insulin, fasting lipids profile (total cholesterol, LDL, HDL, triglycerides), INR, PTT, ALT, AST, ALP, total bilirubin, direct bilirubin, albumin, CRP, B12, ferritin

++Eating and weight patterns questionnaire + hospital anxiety and depression questionnaires (only at baseline), Impact of Weight on Quality of Life-Lite (IWQOL-Lite), Short Form (36) Health Survey (SF36), Patient Health Questionnaire 9 (PHQ9), Pittsburg Sleep Quality Index (PSQI), Three Factor Eating Questionnaire (TFEQ)

† To occur after all screening assessments are complete; within 45 days of screening evaluations

† † To discuss upcoming post-op diet and exertion

◊ If the procedure is unable to be performed within the 105 day in-window range due to factors outside the control of the study team (patient testing positive for COVID-19, delays associated with H. pylori eradication testing, or limitations of the procedural schedule), the PI will assess if any baseline laboratory tests must be repeated prior to the procedure for subject safety.

Participant Retention

All patients will be encouraged to complete study follow-up, and all reasonable efforts will be made to ensure completeness of follow-up.

It is understood that study participants may withdraw consent for study participation at any time irrespective of their reasons. The investigators may also withdraw a participant from the study in order to protect their safety, and/or if they are unwilling or unable to comply with the required study procedures.

In the event of a patient withdrawing from the trial, the reason for withdrawal must be documented on the CRF.

Replacement of withdrawn subjects

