8.2.3 Secondary Analyses

A per-protocol analysis will compare randomized groups among protocol adherent patients – here, defined among as those actually receiving the procedure and making $\geq 80\%$ follow-up visit in both groups. Modified ITT will be considered the primary approach for all efficacy analyses and will include patients who actually received the intervention regardless of adherence to follow-up visits. Safety endpoints and adverse events may be evaluated based on treated group (per-protocol).

Additional outcomes and analyses not specified here are considered exploratory and post-hoc and will be clearly identified as such in any publications.

^b %TBWL defined as $[(\text{pre-operative weight} - \text{post-operative weight}) / (\text{pre-operative weight})] \times 100$

^c % EWL defined as $[(\text{pre-op weight} - \text{follow up weight}) / (\text{pre-op weight} - \text{ideal body weight})] \times 100$

Note: "Ideal body weight" of BMI 25

Missing Data

The primary analysis uses a hierarchical regression model, assuming post-randomization dropout is missing at random (MAR) among subjects completing at least 1 of the planned follow up visits.

Patients excluded after randomization and before intervention on the basis of identified exclusion criteria will be excluded from analyses; reasons for meeting exclusion criteria will be documented. Patients that withdraw/dropout between randomization and intervention are assumed to be missing completely at random. However, a sensitivity analysis will compare withdrawn subjects to participating subjects and perform analyses under MAR (including multiple imputation) assumptions if these subjects appear different or if dropout occurs at substantially different rate in one arm compared to the other. Participating patients who dropout prior to the first follow up visit will be analyzed similarly.

Randomization and Data Collection

Stratified block randomization schedules will be uploaded to REDCap. Data will be collected in REDCap data collection forms.

Interim Analysis

No interim analysis will be performed for efficacy endpoints. Adverse events will be monitored throughout and discussed with the data monitoring committee.

ETHICAL CONSIDERATIONS

This study is to be conducted according to United States government regulations and Institutional research policies and procedures.

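### An unblinded investigator may withdraw a treated participant from the study for non-compliance, and no week-26 endoscopy, weight or adverse-event follow-up is then required

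*Combined protocol and SAP*

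**What the plan says.** Participant Retention gives investigators two grounds for withdrawing someone from the study: to protect the participant's safety, and "if they are unwilling or unable to comply with the required study procedures". Neither ground is limited to the time before the procedure. The one record the section demands is that "the reason for withdrawal must be documented on the CRF". The same section opens with a general promise that "all reasonable efforts will be made to ensure completeness of follow-up", but does not say whether this still applies after withdrawal.

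The Randomization section states: "Research teams will not be blinded to the randomization results".

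Section 8.2.3 makes modified intent-to-treat (mITT) the main approach for efficacy and says that it "will include patients who actually received the intervention regardless of adherence to follow-up visits". Adherence is handled in a secondary analysis: "A per-protocol analysis will compare randomized groups among protocol adherent patients", defined by receipt of the procedure and at least 80% of follow-up visits.

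The Missing Data section describes a hierarchical regression, "assuming post-randomization dropout is missing at random (MAR) among subjects completing at least 1 of the planned follow up visits". For earlier losses it adds: "Participating patients who dropout prior to the first follow up visit will be analyzed similarly". That refers back to the rule for dropout before the intervention: missing completely at random, with a conditional sensitivity analysis under MAR.

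**The concern.** The procedure is given once and its durability is read at one scheduled endoscopy, at week 26. A participant who is treated and then withdrawn for non-compliance before that visit remains in the mITT set by definition, but may contribute no primary outcome. The required procedures are broad. They could be read to include MRI, scintigraphy, questionnaires and counselling, none of which is needed to read the sutures, weigh the participant or ask about adverse events. Someone who declines one of these could therefore leave follow-up altogether while still willing to attend for the rest.

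Two features make such a loss hard to treat as ignorable. Non-compliance may plausibly follow symptoms or disappointing weight loss, so it may be related to outcome. The decision can also be taken by staff who know the arm. At stake are the durability comparison, the 6- and 12-month weight results, and the adverse-event record, on which the safety goal and the event counts in 7.11 Stopping rules depend.

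**Working it through.** **Inputs from the documents.** 24 participants, 12 per arm (Power and Sample Size). Endoscopy at the procedure and at week 26 (Schedule of Events). Follow-up to week 52. Goal of under 5% serious adverse events related to the device or procedure (Safety).

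**Inputs not given.** The plan states no dropout rate, durability rate or expected number of withdrawals. The values below are assumptions, shown as a range. The external video read has three classes (intact, partially intact, open); I assume durability is summarised as a yes/no proportion.

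**Step 1: the plan's own figure.** 24 / 2 = 12 per arm, which agrees. No power calculation was made, so there is nothing further to reproduce.

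**Step 2: the texts side by side.**
- Participant Retention governs who remains in the study; 8.2.3 governs who is analysed. A treated participant who is withdrawn meets both rules: out of the study, in the mITT set.
- The set is then intact on paper, but the week-26 value may not exist. For weight, readings before withdrawal can inform a model under MAR. For durability there is no earlier post-procedure reading to inform one.
- The planned sensitivity analysis also works under MAR. No analysis allows for data missing not at random.
- Replacement runs to 24 participants who have received a procedure, so it does not provide for those withdrawn after treatment.

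**Step 3: best/worst-case width.** If m treated participants in one arm of 12 lack the week-26 endoscopy, that arm's durability proportion is uncertain by m/12:
- m = 1: 1/12 = 8.3 points
- m = 2: 2/12 = 16.7 points
- m = 3: 3/12 = 25.0 points

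**Step 4: completer proportion if all those lost are non-durable.** With x truly durable of 12, the observed value is x/(12 − m):

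| True | 1 lost | 2 lost | 3 lost |
|---|---|---|---|
| 8/12 = 66.7% | 8/11 = 72.7% | 8/10 = 80.0% | 8/9 = 88.9% |
| 6/12 = 50.0% | 6/11 = 54.5% | 6/10 = 60.0% | 6/9 = 66.7% |
| 4/12 = 33.3% | 4/11 = 36.4% | 4/10 = 40.0% | 4/9 = 44.4% |

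If both arms are truly 8/12 and two non-durable participants are lost from one arm only, the observed difference is 80.0 − 66.7 = 13.3 points where none exists. If the same loss occurs in both arms, each proportion is too high but the difference stays at zero.

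**Step 5: safety.** 1/24 = 4.2%, within the goal; 2/24 = 8.3%, outside it. If one related serious event is on record, a second that goes unrecorded after withdrawal changes the result.

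**Step 6: time at risk.** If adverse-event review did stop on withdrawal at, say, week 16, 52 − 16 = 36 weeks would go unobserved.

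**The case against.** The strongest reply is that the two sections do not conflict. A reader might infer a contradiction, but one rule concerns participation and the other the analysis set, and Missing Data expressly anticipates dropout after treatment. That stands: the conflict is practical, not textual.

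A reader might also infer that nothing but the reason is collected after withdrawal. The documents do not say so. The CRF sentence sets a minimum record, does not forbid further data, and sits beside the promise of reasonable efforts at complete follow-up. What stands is narrower: no continued follow-up is required. Nor does anything allow data already collected to be discarded; only future data are at risk.

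It would be wrong, too, to say that withdrawal after the procedure can only end data collection. Trial Intervention provides for a transitional diet, 12 months of omeprazole and a 12-visit lifestyle programme, so non-compliance may bear on safety. The safety ground for withdrawal is separate, however, and is not in question here.

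The documents also have milder routes. Missed visits and tests are listed under Protocol Deviation, and the 80% rule presupposes that less adherent participants stay in the study. The clause is permissive and might never be used after treatment. This lowers the likelihood of loss, but it also shows that the clause is not needed after the procedure in order to deal with non-compliance.

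Finally, the team has no scheduled durability reading before week 26, so it could not select directly on the primary outcome, and the external blinded read protects the assessment of each available video. Neither point settles which videos will exist. Selection through symptoms or weight loss remains possible.

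**Conclusion.** The point holds as a gap that undercuts the mITT aim. A stated discretion, exercisable by staff who know the arm, can end a treated participant's follow-up for non-compliance, and no provision secures the week-26 endoscopy, later weights or adverse-event review. MAR is then doubtful, and for durability there is no earlier reading to support it.

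The firm figure is 8.3 points of best/worst-case uncertainty per missing participant in an arm of 12. The shift from 67% to 80% is an illustration: it assumes an 8/12 rate, two withdrawals and that both are non-durable. A spurious between-arm difference also needs unequal loss. The safety figures assume all 24 treated participants in the denominator.

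The documents do not show that such withdrawals will occur, or that they would be selective. In a 24-participant pilot this is a worthwhile, inexpensive correction and does not invalidate the design.

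**What to change.** In Participant Retention:
- Limit non-compliance as a ground for withdrawal from the study to the period before the procedure.
- State that a treated participant who stops individual study procedures, such as MRI, scintigraphy, questionnaires or counselling, remains in follow-up for the week-26 endoscopy, and for weight and adverse events to week 52, unless consent for that item is withdrawn.
- On the CRF, record stopping some procedures separately from withdrawing consent for all follow-up, with who decided and why, and report these by arm.
- Leave safety-based withdrawal and clinical management as they are.

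The cost is protocol wording and a small CRF change. The assessments are already scheduled, and the Informed Consent section already accepts phone or video contact where possible, which could serve for adverse-event review. The downside is that staff must keep contacting less adherent participants.

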Twenty-four eligible participants will be block-randomized 1 to 1 treatment (12 participants) and control (12 participants) groups. All participants will undergo endoscopy and those without endoscopic contraindications will be eligible. All treatment group subjects will undergo combined HAPC and ESG where APC is applied according to on-label use prior to the standard ESG technique for enhanced fibrosis along the site of the plications potentially providing an avenue for longer and more durable ESG while minimizing the associated complications. Control subjects will undergo traditional ESG alone. All participants will undergo a repeat upper endoscopy at 26 weeks (6 months) +/- 2 weeks to evaluate the durability of the endoscopic sutures. All subjects will undergo research MRI at baseline and 26 weeks +/- 2 weeks to evaluate and grade the durability of the created gastroplasty, gastric motility, and gastric accommodation. This specially developed MRI protocol at Mayo offers a gold standard in evaluating gastroplasty durability. Additionally, at both baseline and 26 weeks +/- 2 weeks, all patients will undergo gastric scintigraphy to evaluate and measure gastric emptying.

Endpoints Effectiveness

Primary:

- Assess durability of endoscopic plications and sutures 26 weeks (6 months) +/- 2 weeks post procedure between patients receiving HAPC/ ESG vs traditional ESG alone.

Secondary:

- %TBWL in the combined HAPC and ESG group compared to traditional ESG at 6 and 12 months.
- Assess the procedure safety.
- % Excess weight loss (EWL) at 6 and 12 months between both groups.
- Proportion with $\geq 25\%$ EWL at 6 and 12 months by randomized arm.
- % of patients in the combined HAPC and ESG group achieving $\geq 5\%$ TBWL at 6 and 12 months compared to ESG alone.
- % of patients in the combined HAPC and ESG group achieving $\geq 10\%$ TBWL at 6 and 12 months compared to ESG alone.
- Changes in quality of life assessed using standard validated questionnaires (IWQOL-lite and SF-36) at 6 and 12 months compared to baseline.
- Changes in depression assessed using PHQ-9 questionnaire at 6 and 12 months compared to baseline.

- Improvement/reduction of hunger and desire to eat evaluated using validated self-reported ratings of appetite based on a 100-mm visual-analogue scale at 6 and 12 months compared to baseline.
- Improvement in eating behaviors evaluated using the Three Factor Eating Questionnaire (TFEQ) at 6 and 12 months compared to baseline.

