- Improvement in obesity related comorbidities (blood pressure, fasting glucose, HbA1c, lipid panel, liver enzymes) at 6 and 12 months compared to baseline.
- Changes in gastric motility, volume, accommodation, and constructed gastroplasty on MRI at 6 months compared to baseline.
- Changes in gastric emptying evaluated by gastric emptying study at 6 months compared to baseline.
- Changes in liver biochemical panel, and glucose homeostasis parameters at 6 months compared to baseline between the two groups.

Safety

- The incidence, frequency, and severity of adverse events related to treatment with the device will be reported throughout the duration of the study.
- Goal is <5% rate of serious adverse events related to the device or procedure (as determined by the site PI). Serious adverse events will be classified in the Adverse Events table.

Study Setting

The study will be conducted at 1 US center, Mayo Clinic in Rochester, MN. The maximum enrollment will be limited to 24 participants. The expected enrollment period is 6 months.

Subjects

Participants will be adult patients (Ages 21 \geq and \leq 65) with a BMI \geq 30 and \leq 40 kg/m² that meet the eligibility criteria below. All eligibility criteria must be met at the time of randomization.

Inclusion Criteria

1. Age 21-65
2. BMI \geq 30 and \leq 40 kg/m²
3. Willingness to comply with the substantial lifelong dietary restrictions required by the procedure.
4. History of failure with non-surgical weight-loss methods.
5. Willingness to follow protocol requirements, including signed informed consent, routine follow-up schedule, completing laboratory tests, and completing diet counseling.

6. Residing within a reasonable distance from the investigator's office and able to travel to the investigator to complete all routine follow-up visits.
7. Ability to give informed consent.
8. Women of childbearing potential (i.e., not post-menopausal or surgically sterilized) must agree to use adequate birth control methods.

Exclusion Criteria

1. History of foregut or gastrointestinal (GI) surgery (except uncomplicated cholecystectomy or appendectomy).
2. Prior gastrointestinal surgery with sequelae, i.e. obstruction, and/or adhesive peritonitis or known abdominal adhesions.
3. Prior open or laparoscopic bariatric surgery.
4. Prior surgery of any kind on the esophagus, stomach, or any type of hiatal hernia surgery.

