All patients will undergo a standard moderate intensity life-style intervention administered over 12 visits in the first year after procedure. Participants will be required to follow up with their prescribing physician to make any necessary changes to their hypertension and/or type II diabetes medications at 3, 6, 9 and 12 months. Completion of patient follow-up with providers for medication adjustment will be captured with completion of the appropriate CRF at the corresponding visits. In the event that participants are unable to contact their physician or participants are experiencing symptoms related to the medication dosing requiring urgent action, the study team will make any necessary changes in their medication dosing and document these changes appropriately in the relevant CRFs. Any medication changes will be monitored and recorded by the study team. Laboratory testing will be obtained as detailed in the study schedule of events

Participants will return for follow-up visits per the schedule of events below. For all visits with the exception of weeks 1 and 4, an in-window visit will be considered as reporting for follow-up visits within a two-week window of the visit date.

At the time of the 6-month visit, each subject's 6-month de-identified EGD video will be shared with an external center for an additional blinded assessment of the primary endpoint (suture durability) by a qualified endoscopist. Each video will be classified objectively according to the aspect of the gastric tissue and the sutures (intact, partially intact, or open). This sharing will take place through Mayo SimpleShare system.

Schedule of Events (SOE)

Study Activity	Screening & Enroll.	Rand.	Procedure	Post-Op Call	Week 1	Week 4	Week 8	Week 12	Weeks 16, 20	Week 26 (Month 6)	Weeks 30, 36, 42, 48	Week 52 (Year 1)	Unscheduled Visit
Visit Number	-2	-1	0	1	2	3	4	5	6,7	8	9,10,11,12	13	
In-Window Day Range	45 to Rand.	60 to Proc.	00		+/- 2	+/- 3				+/- 14			
Informed Consent Form (ICF)	X												
Complete Physical Exam (CPE)*	X											X	X
Focused Physical Exam *					X								
EKG	X												
Formal nutritional assessment	X												
Formal psychology evaluation	X												
Pregnancy test **	X												
Laboratory tests ⁺	X										X		X
H-Pylori breath test (baseline only)													
Questionnaires ++	X							X		X		X	
Inclusion/Exclusion	X												
Procedure Assessment Form			X										
GERD Questionnaire & Activity Assessment Form	X				X	X	X	X	X	X	X	X	X

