Gastric MRI will only be performed in patients who can safely undergo MRI. It will be performed at both baseline and 6 months for subjects randomized to either study arm. Subjects will be kept NPO after midnight and scanned with MRI using a torso phased array coil. If the 3T magnet (Phillips) is not available, a 1.5T magnet will be used. Before, and after a meal (296 ml Ensure mixed with 4ml gadolinium, i.e., 300 ml), static and dynamic imaging sequences will be acquired using available MR sequences to assess respectively gastric volumes and motility. No intravenous contrast will be administered. Postprandial accommodation will be calculated as the difference between postprandial and fasting volumes (Neurogastroenterol Motil 2009; 21:42–51; American Journal of Physiology. 2014;307:G582-G587). Likewise, gastric motility (i.e., contractile frequency, amplitude and velocity) will be analyzed with established approaches (Neurogastroenterol Motil 2011;23(7):617-e252).

Gastric Emptying Scintigraphy

Gastric emptying scintigraphy will be performed at baseline and at 6 months for subjects randomized to either study arm. Imaging will begin immediately after consumption of a standardized meal including 1 mCi Tc-99m labeled sulfur colloid in two eggs accompanied by one slice of white bread and a glass of skim milk. For patients unable to consume any individual component of the meal substitutions will be made according to clinical protocol. Dual isotope acquisition of anterior and posterior views of the abdomen will be acquired, with view times to be within +/- 15 minutes of the hour. Images will be acquired Baseline (0), 1, 2, 3 and 4 hours following ingestion of the radiolabeled meal. Results will be interpreted according to institutionally established normal ranges. Geometric means of decay-corrected counts in anterior and posterior gastric regions of interest will be used to estimate the proportion of 99mTc emptied at each time point.

Screening & Enrollment

This will include a patient visit for procedures mentioned in section 5.3. This includes:

- Signing informed consent form
- Screening exam and intake by the investigator or co-investigator
- Baseline anthropomorphic and vital signs data
- Baseline laboratory testing, including pregnancy test if female of childbearing potential
- Baseline EKG
- Baseline MRI
- Baseline gastric emptying scintigraphy
- Baseline questionnaires.
- Baseline nutritional assessment
- Baseline psychological evaluation and approval

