8.2.1 Primary Aim

The primary outcomes are durability of plications and endoscopic sutures on repeat endoscopy at 6 months, in the two randomized arms.

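### The plan does not say who reads the research MRI or whether that reader is masked to arm, while it declares research teams unblinded and specifies a masked read only for the EGD video.

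*Combined protocol and SAP*

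**What the plan says.** All references are to the combined protocol and SAP.

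- **Study Design, General Description.** "All subjects will undergo research MRI at baseline and 26 weeks +/- 2 weeks to evaluate and grade the durability of the created gastroplasty", together with motility and accommodation. The next sentence reads: "This specially developed MRI protocol at Mayo offers a gold standard in evaluating gastroplasty durability".
- **Endpoints, secondary list.** One secondary endpoint is "Changes in gastric motility, volume, accommodation, and constructed gastroplasty on MRI at 6 months compared to baseline".
- **8.2.1 Primary Aim.** The primary outcome is endoscopic: "The primary outcomes are durability of plications and endoscopic sutures on repeat endoscopy at 6 months".
- **Measurement of Gastric Accommodation by Dynamic MRI.** This covers preparation, magnet, test meal and sequences, then states "Postprandial accommodation will be calculated as the difference between postprandial and fasting volumes". Motility is to be analysed by approaches given by citation. No reader is named, and neither masking nor a scale for the gastroplasty grade is mentioned.
- **Randomization.** "Research teams will not be blinded to the randomization results". The same paragraph promises masking procedures in general terms and keeps the assignment out of the EMR to limit what the clinical team learns during follow-up.
- **Trial Intervention.** For endoscopy, each participant's "6-month de-identified EGD video will be shared with an external center for an additional blinded assessment" of the primary endpoint. The Schedule of Events and the Week 26 visit list repeat this read. No other masked read appears in the document.

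**The concern.** Two modalities address durability at 6 months, endoscopy and MRI. For endoscopy the plan guards against reader expectation by having de-identified video assessed at an external center. For MRI, which it ranks as a gold standard on the same question, it specifies no such guard.

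Grading a gastroplasty calls for judgement, and a reader who knows which participants had HAPC may, without intending to, grade or measure in the expected direction. If the week-26 MRI were read that way, a difference favouring HAPC could not serve as independent corroboration of the endoscopic result. Once scans have been read with the arm known, only a repeat masked read repairs the data.

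**Working it through.** The plan states no figure on this point, so there is nothing to reproduce. The check is of the text, followed by one hypothetical calculation.

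**Step 1. Does the MRI endpoint involve a reader's judgement?** For the grade, yes: the General Description uses the MRI "to evaluate and grade the durability of the created gastroplasty, gastric motility, and gastric accommodation", and no scale is given. For volumes and motility, the plan does not say how automated the analysis is.

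**Step 2. Who reads the MRI?** Not stated. The MRI section is in the passive voice throughout. The label research MRI makes a research reader plausible, but a reader outside the research team also fits the text.

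**Step 3. Does any rule mask that reader?**

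| Provision | Does it cover the MRI reader? |
|---|---|
| Research teams unblinded (Randomization) | No exception for image readers |
| General promise of masking (Randomization) | Names no role and no assessment |
| Assignment kept out of the EMR (Randomization) | Stated aim is to limit the clinical team's exposure in follow-up care |
| EMR source required for the procedure (Source Documentation) | A procedure record could reveal the arm to a reader with EMR access (inference) |
| External blinded read (Trial Intervention) | EGD video only |

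No provision requires a masked MRI read, and one leaves any reader in the research team unblinded.

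**Step 4. What could a shift do? Hypothetical only.** From the plan: 12 per arm. Assumed, because the plan gives no MRI variability, no alpha and no test for MRI outcomes: a two-sample t-test, two-sided 5%, no true effect, and a reader-induced difference of b SD between arms.

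Degrees of freedom = 2 × 12 − 2 = 22. Noncentrality = b × √(12/2) = 2.449 b. The rejection probability comes from the noncentral t distribution.

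| b (SD) | Noncentrality | False-positive rate |
|---|---|---|
| 0 | 0 | 5.0% |
| 0.10 | 0.245 | 5.6% |
| 0.25 | 0.612 | 9.0% |
| 0.50 | 1.225 | 21.6% |
| 0.75 | 1.837 | 42.0% |

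Nothing in the documents says which row, if any beyond the first, would apply. Two features could make the effect smaller:

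- The endpoint is change from baseline, and the baseline scan precedes randomization. If it is read before randomization, that reading cannot be influenced by the arm.
- Accommodation is a difference A = V(post) − V(fasting). A common proportional error e turns it into (1 + e)A, a shift of eA rather than e × V(post). A constant offset in both volumes cancels.

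**The case against.** The strongest reply is that the plan nowhere gives the MRI read to unblinded staff. A reader might infer that it does, by joining the term research MRI to the statement on research teams. The documents do not support that step, because the MRI reader is never identified. A radiologist without the assignment is compatible with every sentence. This stands, and it limits the point to what the plan permits.

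The masking sentence and the EMR rule also show that the authors had bias in mind. Both bear on what a reader might know, but neither reaches the MRI read: the first names no assessment and the second is aimed at follow-up care.

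It can also be said that the accommodation formula is only a subtraction and that the measurements may be largely automated. That is fair. The sentence marks where a masking rule belongs and does not itself show a defect. For volumes and motility, dependence on the reader is possible but not documented. For the grade, it follows from the plan's own wording.

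Finally, MRI is one of many secondary endpoints in a 24-patient pilot for which the plan considers no power calculation warranted, and the primary endoscopic outcome has its own external blinded read. This also stands and bears on severity. A reader might extend the concern to the primary result, but nothing in this gap touches it.

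**Conclusion.** The concern holds as a gap in masking. The plan makes MRI a secondary durability endpoint and calls it a gold standard. It does not say who reads it or whether that reader is masked, declares research teams unblinded without exception, and specifies a masked read for the EGD video alone. Followed as written, it allows the week-26 grade and measurements to be made with knowledge of the arm. The consequence is a weaker claim that MRI independently supports the endoscopic outcome.

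The size of any bias cannot be estimated from the documents. The error rates above rest wholly on assumed shifts and an assumed test. A reader might take them as evidence that the MRI comparison will be biased, but they show only how a shift would act with 12 per arm. The change should be made because it is cheap and is best in place before the first week-26 scan is read. It is not a flaw that endangers the primary analysis.

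**What to change.** Add to the MRI section, in substance:

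> Baseline and week-26 MRI data sets are exported under a study code with identity, arm and procedure details removed. Volumes, accommodation, motility and the gastroplasty grade are derived by the analysts who would otherwise read them, without access to the randomization field or the procedure record. Results are locked before the code is linked to arm.

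Amend the Randomization section so that MRI readers are exempt from the statement that research teams are unblinded. At lower priority, extend the exemption and the coding to those who draw the scintigraphy regions of interest. Leave the EGD read as the Trial Intervention section specifies it.

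The cost is a few sentences and a coded export, with no additional scan. The downside is that the MRI reader cannot be the procedure endoscopist or anyone who holds the assignment. Because the plan names no reader, the site should confirm that its intended reader meets this condition. If so, no extra reader is needed.
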